### Sample size:

We are planning a study of a continuous response variable from independent controls and experimental subjects with one control per experimental subject. In a prior study looking at pain associated with intradetrusor botox, the response within each group had a standard deviation of 2.08. If the true difference between the experimental and control groups is 1.4 which would represent a 38% difference in pain scores, then we would need to enroll 36 controls and 36 experimental subjects to reject the null hypothesis that the population means of the experimental and control groups are equal with a probability (power) of 0.8. The type 1 error probability associated with this test of this null hypothesis is 0.05.

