**B2. SIGNIFICANCE AND BACKGROUND FOR THE STUDY**

Lidocaine is a commonly used amide-type local anesthetic. Lidocaine exists as both a quaternary water soluble structure, and a tertiary lipid-soluble structure. Only the tertiary lipid-soluble structure can cross the lipid bilayer of a cell membrane and thereby enter a neurons axoplasm and induce the desired effect. The ionization constant of lidocaine is 7.7 which means that at a pH of 7.7, 50% of lidocaine is available in the tertiary lipid-soluble structure. At a physiologic pH between 7.35 and 7.45 only around 44% of lidocaine is in the tertiary lipid-soluble structure. However, for lidocaine to be stable in solution, it is typically formulated as a hydrochloride salt and the pH of most commercially available lidocaine solutions are at a pH of 6.09. In an acidic solution the majority of lidocaine is available in the quaternary water-soluble structure and at this pH only 2.5% of lidocaine is in the tertiary lipid-soluble structure. A Cochrane review found that increasing the pH of lidocaine prior to injection decreased pain and increased patient satisfaction perhaps because of the aforementioned pharmacokinetic principles

Lidocaine is typically used as anesthetic for intradetrusor injections of onabotulinum toxin A for the treatment of refractory overactive bladder. In 2003, a technique for intradetrusor injections of onabotulinum toxin A was first described using only local anesthesia. At that time, the procedure involved intrauterthral lidocaine. The procedure has evolved since that time and currently many physicians utilize protocols with both

utraurethral and intravesical lidocaine. At baseline intradetrusor onabotulinum toxin A injections are generally well tolerated and with reported mean VAS scores around 3.

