### Outcome Measures:

The **primary** outcomes measures will include:

- Pain: The Visual Analogue Scale (VAS) consists of a straight line with the endpoints defining extreme limits such as 'no pain at all' and 'pain as bad as it could be' which was first described in 1923. The patient is asked to mark his pain level on the line between the two endpoints. The distance between 'no pain at all' and the mark then defines the subject's pain. Studies vary on the definition of a clinically meaningful change in pain, but suggest that a difference of anywhere from 12% to 38% may be clinically significant

The **secondary** outcomes measures will include

- Satisfaction
- Willingness to undergo repeat procedure
- Adverse events
  - Adverse events will be collected from the medical record and include postoperative urinary tract infections, hematuria, readmission, urinary retention, number of patient phone calls
- Pelvic Floor Distress Inventory (PFDI-20) Scores
  - The short-form version of the Pelvic Floor Distress Inventory has a total of 20 questions and 3 scales (Urinary Distress Inventory, Pelvic Organ Prolapse Distress Inventory, and Colorectal-Anal Distress Inventory). Total PFDI score measured on a 0-300 scale with higher scores equal to greater pelvic floor distress. As with the Total PFDI Score, higher subscale scores equal greater pelvic floor distress, on a 0-100 scale

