**B. Statistical Considerations**

This is a prospective double-blinded randomized controlled trial comparing two pre-treatment protocols for patients undergoing intradetrusor botox injections to determine if a buffered lidocaine solution offers superior pain control. We are planning as study of a continuous response variable from independent controls and experimental subjects with one control per experimental subject. In a prior study the response within each group had a standard deviation of 2.08. If the true difference between the experimental and control groups is 1.4 which would represent a 38% difference in pain scores, then we would need to enroll 36 controls and 36 experimental subjects to reject the null hypothesis that the population means of the experimental and control groups are equal with a probability (power) of 0.8. The type 1 error probability associated with this test of this null hypothesis is 0.05.

All de-identified data will be shared with BIDMC who will help with the statistical analysis. We will analyze data with SAS 9.3 (SAS Institute, Cary, North Carolina). Descriptive statistics will be presented as medians with interquartile range (IQR), median with standard deviation or proportions, depending on data type and distribution. We estimate the risk ratio (RR) and 95% confidence interval (CI) for pre-specified risk factors. All tests will be two sided and P values <0.05 will be considered statistically significant.

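### Does the 38% attached to the 1.4-point target undermine the sample size, when the background section puts mean VAS at about 3?

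*Combined protocol and SAP*

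**What the plan says.** The target appears in the protocol under *Sample size* and again, almost word for word, under *B. Statistical Considerations*. The premise is "If the true difference between the experimental and control groups is 1.4 which would represent a 38% difference in pain scores". The spread comes from one earlier study: "In a prior study looking at pain associated with intradetrusor botox, the response within each group had a standard deviation of 2.08". The second section repeats this more briefly: "In a prior study the response within each group had a standard deviation of 2.08". Neither section cites that study, gives its mean, or says what the 38% is a percentage of. The error rate is 0.05, two-sided ("All tests will be two sided and P values <0.05 will be considered statistically significant"), the power is 0.8, allocation is 1:1, and the result is 36 per arm.

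Two other statements bear on the percentage. The background (B2) calls the injections "generally well tolerated and with reported mean VAS scores around 3", citing three reports. *Outcome Measures* says of earlier work that studies "suggest that a difference of anywhere from 12% to 38% may be clinically significant". So 38% is the top of the range that the plan itself treats as possibly meaningful.

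**The concern.** The 38% is the only bridge between the target in points and the plan's statement of what may matter to patients, which is given in percent. The only mean VAS in the document does not reproduce it. At a control mean of 3, the 1.4-point target is a 47% reduction, above the whole 12% to 38% range.

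If control pain really averaged 3 with SD 2.08, a true 38% reduction would give a non-significant result 37% of the time rather than 20%. A negative trial might then be read as ruling out a benefit that the plan calls meaningful. Restoring 80% power for that effect would take 54 per arm, 108 patients instead of 72.

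**Working it through.** **Inputs.** Difference 1.4, SD 2.08, power 0.8, alpha 0.05 and 36 per arm (*Sample size*); two-sided testing (*B. Statistical Considerations*); mean VAS about 3 (B2); 12% to 38% (*Outcome Measures*).

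**1. The plan's own figure.** The normal approximation is n = 2(z₀.₉₇₅ + z₀.₈₀)² × (SD/Δ)² = 2 × (1.960 + 0.842)² × (2.08/1.4)² = 34.7, so 35 per arm. The two-sample t-test (noncentral t, 2 × 36 − 2 = 70 degrees of freedom) has noncentrality 1.4/(2.08 × √(2/36)) = 2.86. It gives 80.4% power at 36 per arm, and 36 is the smallest number that reaches 80%. The stated sample size is reproduced.

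**2. The mean implied by 38%.** 1.4/0.38 = 3.68. Allowing for rounding of both figures, the limits are 1.35/0.385 = 3.51 and 1.45/0.375 = 3.87. Other bases fit B2 less well. A percentage of the average of the two arms needs a control mean of 1.4/0.38 + 0.7 = 4.38, and a percentage of the treated mean needs 1.4/0.38 + 1.4 = 5.08. On an assumed 0–10 scale (the document does not give the length), 1.4 is 14%. The natural reading is therefore a control mean near 3.7.

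**3. What if the mean were lower and the SD stayed at 2.08?** Noncentral t, 36 per arm:

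| Control mean | 1.4 as % of mean | 38% in points | Power for 38% | Per arm for 80% |
|---|---|---|---|---|
| 2.5 | 56% | 0.95 | 48% | 77 |
| 3.0 | 47% | 1.14 | 63% | 54 |
| 3.49 | 40% | 1.33 | 76% | 40 |
| 3.68 | 38% | 1.40 | 80% | 36 |

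**4. What if the SD moves with the mean?** Scaling gives SD = 2.08 × 3/3.684 = 1.69. The standardised difference is then 1.14/1.69 = 0.67, the same as 1.4/2.08 = 0.67, and power is again 80.4%. In between, at a mean of 3, an assumed SD of 1.8 gives 76%; an assumed SD of 2.3 gives 55%.

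**5. Do the two means describe the same thing?** B2 summarises three cited reports in one approximate phrase. *Sample size* draws on a single, uncited study. It may or may not be one of the three. Either way, a study with a mean near 3.7 can sit among reports loosely described as about 3. Nothing in the document names 3 as the control mean used for planning.

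**The case for a change.** The strongest case for acting is that the percentage carries weight. *Outcome Measures* gives no threshold in points, so without the 38% nothing in the document ties 1.4 points to clinical relevance. At SD 2.08, every control mean that rounds to 3 leaves power for a 38% reduction below 80% (48% to 76%). A smaller SD would restore power but not the label, since 1.4 would still be 47% of 3. One sentence giving the source mean would settle the matter.

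Part of this stands. The control mean, its source and the base of the percentage are missing, and the implied 3.68 is somewhat above the figure in B2. The rest is weaker. Strict integer rounding asks too much of a loose summary, and even so the two ranges almost touch (3.49 against 3.51). The 63% needs both a mean of 3 and an unchanged SD, and the document sets neither that mean nor that pairing as a planning assumption. The claim that the target lies above the meaningful range also assumes that 12% to 38% is relative to the control mean. *Outcome Measures* does not say so, and on an assumed 0–10 scale 1.4 points is 14%, inside the range.

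**Conclusion.** No change to the plan follows. Power is promised for a difference of 1.4 points at SD 2.08, and 36 per arm provides 80.4%. The plan makes no claim of 80% power for a 38% reduction from a mean of 3, so the 63% contradicts no stated figure. It is a scenario built from a mean and an SD that may come from different studies, and it returns to about 80% if the SD scales with the mean.

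The surviving gap is one of reporting. A reader can recover the implied control mean of 3.68 but cannot check its source. Writing it down, or relabelling 38% as 47%, would leave the sample size, the test and the reading of the result as they are. Once the trial is complete, the observed control mean and SD will show what percentage any difference represents. Going to 54 per arm would add 36 patients on the strength of a planning mean that the document does not adopt.

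This rests on reading the 38% as relative to the control mean and on taking 2.08 as the correct SD for the source study; the document alone cannot confirm either.

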### Study period:

November 2019 through November 2021

**Data collection:**

Baseline characteristics collected from the medical records and collected as part of routine clinical care for every patient:

- Age (years),
- Gravid (numeric value),
- Para (numeric value),
- BMI (height and weight)
- Race/ethnicity
- Medical history (fibromyalgia, use of chronic pain medications, chronic back pain)
- Surgical history (hysterectomy, prolapse surgery, urinary incontinence surgery)
- Pre-treatment Kegel strength
- Pre-treatment myofascial pain
- Pre-treatment POPQ
- Pre-treatment PFDI-20

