**Secondary Objectives:**

1. Patient satisfaction measured on a five point Likert scale
2. Willingness to undergo procedure again measured on a five point Likert scale
3. Adverse events
4. Demographic and clinical factors that predict high pain scores during the procedure

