### B3. DESCRIPTION OF RESEARCH PROTOCOL

#### A. Study Design – Overview, Methods, Procedures

**Brief overview:** This will be a prospective double-blinded randomized controlled trial comparing two pre-treatment protocols for patients undergoing intradetrusor botox injections to determine if a buffered lidocaine solution offers superior pain control.

**Study Protocol:** After approval by the IRB, providers will approach possible participants who are having intradetrusor botox injection for overactive bladder which is the standard of care for patients with refractory overactive bladder. If the patient meets eligibility criteria, consent forms will be signed and the patient will be randomized 1:1 to receive either our standard pretreatment regimen with 50 mL 1% lidocaine + 50ml of 0.9% normal saline or our buffered bicarbonate protocol with 50 mL 1% lidocaine + 45ml of 0.9% normal saline + 5 mL 8.4% sodium bicarbonate. The primary end point of this trial is to assess the pain scores measured on a Visual Analogue Scale (VAS) immediately following the procedure. Secondary end points include patient satisfaction, willingness to undergo repeat treatment and adverse events.

All subjects will be randomized 1:1 at the first intervention visit to one of the two protocols . At the completion of the procedure, patients will be asked to complete a brief questionnaire about their experience. Patients will follow up in clinic for a post-void residual check two weeks after the procedure as is standard for

MOUNT AUBURN  
HOSPITAL

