**Exclusion criteria:**

1. Urinary retention requiring intermittent self catheterization
2. Neurogenic bladder
3. Requiring pretreatment with anxiolytic or opiate prior to in-office procedure

MOUNT AUBURN  
HOSPITAL

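### A single pain mark before the instillation would let objective 4 tell procedural pain from background pain, and might sharpen the primary comparison at almost no cost

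*Combined protocol and SAP*

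**What the plan says.** **Outcome and timing.** The overview in B3.A defines the primary endpoint as "pain scores measured on a Visual Analogue Scale (VAS) immediately following the procedure". The only patient-completed form described there comes at the end of the visit: "At the completion of the procedure, patients will be asked to complete a brief questionnaire about their experience". Under Outcome Measures, the scale is described in general terms: "The patient is asked to mark his pain level on the line between the two endpoints".

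**Baseline data.** The Data collection section introduces its list as "Baseline characteristics collected from the medical records and collected as part of routine clinical care for every patient". The list includes "Medical history (fibromyalgia, use of chronic pain medications, chronic back pain" and "Pre-treatment myofascial pain", the latter with no scale or timing stated. It contains no VAS and no other same-day pain rating.

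**Eligibility.** Neither list of exclusion criteria names chronic pain. The nearest item, in B3.C, is "Requiring pretreatment with anxiolytic or opiate prior to in-office procedure", which concerns premedication for the procedure.

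**Objective and analysis.** The fourth secondary objective in B1 is "Demographic and clinical factors that predict high pain scores during the procedure". The only matching analysis text, in B3.B, is a risk ratio with a 95% confidence interval for pre-specified risk factors. It gives no list of those factors, no cut-off for a high score and no adjustment. B3.B names no model or covariate for the primary comparison either.

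**The concern.** Several candidate predictors for objective 4 (fibromyalgia, chronic back pain, chronic pain medication, myofascial pain) are markers of pain that a woman may already have when she arrives. The outcome is one mark made afterwards, and nothing on the same scale precedes it. If the mark reflects everything the patient feels at that moment, a woman who arrives at 3 and leaves at 3 is recorded exactly like one who arrives at 0 and is brought to 3 by the injections. A raised risk ratio for fibromyalgia could then mean that the procedure hurts these women more, or only that they had more pain beforehand.

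The two readings have different uses. The first says whose procedure needs better pain control. The second says nothing about the procedure. A rating not taken on the day cannot be recovered later. The primary comparison also gives up a covariate that might explain part of the between-patient variation.

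**Working it through.** **1. The plan's own figure.** Inputs from Sample size and B3.B: SD 2.08, difference 1.4, two-sided alpha 0.05, power 0.80, 1:1 allocation. The two-sample t-test solution is 35.64 per arm, which rounds up to the stated 36. The normal approximation gives 2 × (1.96 + 0.8416)² × 2.08² / 1.4² = 34.65, or 35. Power at 36 per arm (t-test) is 0.804. The stated sample size reproduces.

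**2. What a baseline covariate could add to the primary comparison.** The documents give no correlation r between pre- and post-procedure VAS, so r is an assumption and is shown as a range.

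- Residual SD = 2.08 × √(1 − r²)
- 95% CI half-width = 1.96 × residual SD × √(2/36)
- Power: two-sample t-test for 1.4 points at 36 per arm, using the residual SD

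| Assumed r | Residual SD | Power | Half-width |
|---|---|---|---|
| 0 (unadjusted) | 2.08 | 0.804 | 0.96 |
| 0.1 | 2.07 | 0.808 | 0.96 |
| 0.2 | 2.04 | 0.820 | 0.94 |
| 0.3 | 1.98 | 0.839 | 0.92 |
| 0.4 | 1.91 | 0.867 | 0.88 |
| 0.5 | 1.80 | 0.902 | 0.83 |

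The degree of freedom spent on the covariate (69 instead of 70) changes these powers by less than 0.001.

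**3. How background pain could appear in objective 4.** This is an illustration, not an estimate. The control mean implied by the sample-size text is 1.4 / 0.38 = 3.68. Assume normal scores with SD 2.08, and suppose a chronic-pain history raises the mark only through pain already present. The shift and the cut-off for high pain are both assumed, because the documents give neither. The risk ratio is P(score > cut-off with the shift) / P(score > cut-off without it).

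| Assumed shift | RR, cut-off 4 | RR, cut-off 5 |
|---|---|---|
| 0.5 | 0.535 / 0.440 = 1.22 | 0.347 / 0.264 = 1.32 |
| 1.0 | 0.629 / 0.440 = 1.43 | 0.440 / 0.264 = 1.67 |
| 2.0 | 0.791 / 0.440 = 1.80 | 0.629 / 0.264 = 2.39 |

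If no background pain carries over, the shift is 0 and the RR is 1. The table shows only that modest carry-over would be visible on the planned scale of analysis. It does not show that carry-over occurs.

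**The case against.** The strongest reply is that the plan already names the construct. The primary objective in B1 is procedural pain associated with the injections, objective 4 refers to pain during the procedure, and the questionnaire asks about the patient's experience. The line about marking a pain level sits in a generic account of how a VAS works, and the wording of the form itself is not in the documents. If the form asks about the procedure, a woman with background back pain and a painless procedure should mark near zero. This stands in part: carry-over is possible but not established.

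Second, objective 4 asks what predicts high scores. If women with fibromyalgia score higher, fibromyalgia predicts high scores by whatever route. Resting pain may lie on the path from the condition to the score, so conditioning on it changes the question and could hide a useful predictor. This stands, and it is why both analyses should be reported.

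Third, the recorded myofascial pain and pain history permit some stratification or adjustment. This also stands in part. Those items come from records or routine care, have no stated link to the VAS, and no adjustment for them is planned.

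A reader might infer that objective 4 cannot be answered, that chronic-pain factors will show a spurious effect of a point or two, or that the treatment comparison is compromised. The documents support none of these. The descriptive question can be answered, any size of carry-over is assumed rather than derived, and randomisation balances background pain between arms in expectation.

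**Conclusion.** This is a cheap improvement, not a flaw that threatens the trial. The visible plan has no same-day, same-scale pain rating before the procedure, although women with chronic pain may enrol and their conditions are recorded. If background pain carries into the post-procedure mark, associations between those conditions and high scores cannot be reliably attributed to the procedure. They remain valid descriptive predictors.

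The primary comparison is unbiased, and 36 per arm delivers the stated power. The possible gain there is precision only: from almost nothing at r = 0.1 (power 0.808) to a useful amount at r = 0.5 (0.902), with no figure in the documents to say where r lies.

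Parts of the public text were not available, so a baseline VAS described there cannot be ruled out. The outcome and baseline lists that are visible show none.

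**What to change.** Add one VAS mark to the baseline list under Data collection, taken after consent and before the instillation. Then:

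- Pre-specify it in B3.B as a covariate in the between-arm comparison of post-procedure VAS.
- For objective 4, report each predictor both without and with adjustment for the pre-procedure VAS. State that the unadjusted result addresses who reports high scores, and the adjusted result addresses who does so given the pain present beforehand.

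Cost: a few seconds of patient time at a visit already attended (B6 places consent before the cystoscopy), one line on a form and one degree of freedom. No extra staff, visit or procedure is needed, and the sample size need not change. If r is low, the primary comparison gains little.

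### The primary VAS comparison makes no stated use of the pain-related baseline variables already recorded; pre-specified adjustment would be a nearly free, modest gain in precision, not the repair of a validity error

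*Combined protocol and SAP*

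**What the plan says.** - **Baseline data.** The Data collection section lists "Medical history (fibromyalgia, use of chronic pain medications, chronic back pain" among the items taken from the record for every patient, and lists pre-treatment myofascial pain separately.
- **Eligibility.** Neither list of criteria excludes chronic analgesic users. The nearest rule, in Subject Selection, concerns patients who need an anxiolytic or opiate before the office procedure.
- **Stated interest in predictors.** The fourth secondary objective is "Demographic and clinical factors that predict high pain scores during the procedure".
- **Design of the primary comparison.** The Sample size section says "the response within each group had a standard deviation of 2.08" and continues "If the true difference between the experimental and control groups is 1.4 which would represent a 38% difference in pain scores", giving 36 per arm. Randomization is 1:1, and no stratification factor is stated.
- **Analysis.** Section B3.B gives one analysis that involves baseline factors: "We estimate the risk ratio (RR) and 95% confidence interval (CI) for pre-specified risk factors". The factors are not named. The section adds "All tests will be two sided and P values <0.05 will be considered statistically significant" but names no test or model for the primary VAS comparison, adjusted or unadjusted.

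**The concern.** The endpoint is a single self-reported pain score in 72 patients. Background analgesic use, and the pain conditions that it marks, are plausible predictors of that score, and the data will already be in hand. If they do predict VAS, leaving them out of the primary model keeps avoidable variance in the error term and widens the confidence interval. The design has little slack: power is just above 80% at exactly 36 per arm, and no dropout allowance is stated.

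Pre-specification is also at stake. Suppose the plan is silent and analgesic users fall unevenly between the arms. The investigators must then either leave the imbalance in the estimate or adjust after the fact, with many baseline variables to choose from.

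**Working it through.** **Inputs from the documents.** Difference 1.4, SD 2.08, 36 per arm and 1:1 allocation (Sample size). Two-sided alpha 0.05 (Sample size and B3.B). Target power 0.8 (Sample size).

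**Inputs not in the documents, assumed.** Share of chronic pain medication users p = 0.2 (range 0.1 to 0.5). VAS difference between users and others b = 1.0 to 1.5 points (range 0.5 to 2.0).

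**Step 1: the plan's own figure.** The normal formula gives n = 2 × [2.08 × (1.960 + 0.842) / 1.4]² = 34.65, so 35 per arm. The exact two-sample t-test gives 35.64, so 36 per arm, which matches the plan. Power at 36 per arm is 80.4%.

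**Step 2: unadjusted precision.** SE = 2.08 × √(2/36) = 0.490. With 70 df the t quantile is 1.994, so the 95% half-width is 0.98.

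**Step 3: adjustment for one binary covariate.** R² = p(1−p)b² / 2.08², residual SD = 2.08 × √(1−R²), tested on 69 df. For p = 0.2:

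| b (VAS points) | R² | Residual SD | SE | 95% half-width | Power |
|---|---|---|---|---|---|
| unadjusted | – | 2.08 | 0.490 | 0.98 | 80.4% |
| 0.5 | 0.009 | 2.07 | 0.488 | 0.97 | 80.8% |
| 1.0 | 0.037 | 2.04 | 0.481 | 0.96 | 81.8% |
| 1.5 | 0.083 | 1.99 | 0.469 | 0.94 | 83.7% |
| 2.0 | 0.148 | 1.92 | 0.453 | 0.90 | 86.2% |

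Over the whole grid, power runs from 80.6% (p = 0.1, b = 0.5) to 89.5% (p = 0.5, b = 2.0). The number needed per arm by the normal formula is 27 to 35, so 36 is never too few.

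**Step 4: chance imbalance is already inside the standard error.** For p = 0.2, the between-arm difference in the share of users has SD √(2 × 0.2 × 0.8 / 36) = 0.094. With b = 1.5 it moves the estimated effect with SD 1.5 × 0.094 = 0.141, or 1.96 × 0.141 = 0.28 points either way in 95% of trials. In variances, 0.141² = 0.020. The unadjusted variance is 0.490² = 0.240 and the adjusted one 0.469² = 0.220. The difference is the same 0.020, so the 0.28 is part of the 0.98 half-width and not an addition to it.

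**Step 5: validity of the unadjusted test.** A simulation of 40,000 trials with p = 0.2, b = 1.5 and total SD 2.08 gave type I error 0.049, power 0.808 and a mean estimate of −1.40 against a true −1.4.

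**Step 6: cost if the covariates explain nothing.** With two covariates (68 df) and R² = 0, power goes from 80.41% to 80.38%.

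**The case against.** The strongest reply is that nothing here is an error. A reader might infer that chance imbalance in analgesic use goes uncorrected and distorts the result. The documents do not support that: allocation is randomized 1:1, and steps 4 and 5 show that the unadjusted standard error and alpha already allow for such imbalance. Setting the 0.28-point shift against the 1.4-point target, as 20% of it, would overstate the matter for the same reason. This part of the objection stands in full.

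A reader might also infer that chronic pain medication is known to affect procedural VAS. No section says so. It appears only as a baseline item, and the secondary objective sets out to find predictors without naming this one. The direction is open too: analgesics may lower scores while the conditions behind them raise them, so a yes/no variable that mixes both could explain almost nothing. This stands, and it is why the gain is given as a range under assumptions.

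A third reading is that the plan has chosen an unadjusted analysis. It has not. The two-means calculation is a sample-size formula, and B3.B names no primary method. That is the larger gap, and covariate choice sits within it. Preferring medication use and myofascial pain to fibromyalgia or back pain is a judgement. The protocol also gives no scale for myofascial pain and no definition of chronic pain medication, so their coding would have to be written.

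The objection does not remove the efficiency argument. The variables are collected in any case, the loss if they are useless is under 0.1 power point, and the sentence naming the primary analysis has to be written anyway.

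**Conclusion.** The point holds as an efficiency and pre-specification improvement. As far as the readable text shows, the plan makes no use of its pain-related baseline variables in the primary comparison. A pre-specified adjusted model would probably gain a little and could lose almost nothing. With 20% users and a difference of 1.0 to 1.5 points, both assumed, the gain is about 1.4 to 3.3 power points and 0.02 to 0.04 VAS points of half-width. It would be negligible if the variables do not predict VAS, and larger if several of them do. The planned 36 per arm is reproduced and stays adequate without adjustment. The documents support no finding of bias, alpha inflation or an undersized trial on this ground.

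**What to change.** In B3.B, state that the primary analysis is a linear model of VAS on treatment arm plus a small set of pain-related baseline covariates already collected, for example use of chronic pain medications (yes/no) and pre-treatment myofascial pain. Define each covariate and its coding, fix the set before unblinding, and do not select covariates by tests of baseline differences. Report the adjusted mean difference with its 95% CI and the unadjusted difference beside it.

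The cost is a few sentences, including the coding, and about two of the 70 degrees of freedom if each covariate enters as a single term. No new data are needed, and sample size and eligibility are unchanged.
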